4.4.5 Relative BA and FE Cohort (Cohort 17)

Cohort 17 will be administered in 3 single-dose regimens in a 3-way crossover design to 12 male and female subjects using 10 mg oral dose treatments. Subjects will receive a TAK-071 10 mg single oral regimen on Day 1 of each period. TAK-071 tablet or DIC will be administered with 240 mL of water.

Regimen A – Fasted State and Capsule Formulation (10 mg in DIC formulation)

Subjects will be fasted overnight for at least 8 hours. Treatment will be administered orally with 240 mL of water. No food should be allowed for at least 4 hours postdose. Water can be allowed after 2 hours postdose.

Regimen B – Fasted State and Tablet Formulation (10 mg [2× 5 mg] tablet formulation)

Subjects will be fasted overnight for at least 8 hours. Treatment will be administered orally with 240 mL of water. No food should be allowed for at least 4 hours postdose. Water can be allowed as desired after 2 hours postdose.

Regimen C – Fed State and Tablet Formulation (10 mg [2× 5 mg] tablet formulation)

Subjects will be fasted overnight for at least 8 hours. After this time, subjects should start the standard high fat meal (~50% fats) 30 minutes prior to administration of the drug product. Study subjects should eat this meal in 25 minutes or less. Drug product should be dosed 30 minutes after the start of the meal with 240 mL of water. No food should be allowed for at least 4 hours postdose. Water can be allowed as desired after 2 hours postdose.

Four subjects will be randomly assigned to 1 of 3 sequence groups and receive the regimens in the order shown in [Table 4.b](#).

Table 4.b Sequence Groups and Regimen Assignment for Cohort 17

Sequence Group	Number of Subjects	Period 1 Day 1	Period 2 Day 1	Period 3 Day 1
1	4	A	B	C
2	4	B	C	A
3	4	C	A	B

Regimen A: Fasted State and Capsule Formulation (10 mg in DIC formulation).

Regimen B: Fasted State and Tablet Formulation (10 mg tablet formulation).

Regimen C: Fed State and Tablet Formulation (10 mg tablet formulation).

5.0 ANALYSIS ENDPOINTS

5.1 Primary Endpoints

The following safety parameters will be analyzed as primary endpoints:

- Percentage of subjects who have at least 1 treatment-emergent adverse event (TEAE).
- Percentage of subjects who meet the Takeda markedly abnormal value (MAV) criteria at least once postdose for the following:
 - Clinical laboratory parameters.
 - Vital sign measurements.
 - ECG parameters.

PK parameters of TAK-071 in plasma following a single dose (Day 1) and at steady-state (after the final dose following multiple dosing) will be analyzed as primary endpoints:

- t_{\max} .
- C_{\max} in plasma.
- Area under the plasma concentration-time curve from time 0 to 24 hours (AUC_{24}).
- Area under the plasma concentration-time curve from time 0 to infinity, calculated using the observed value of the last quantifiable concentration (AUC_{∞}) (single dose only [Day 1]).

5.2 Secondary endpoints

Plasma and urine PK parameters of TAK-071 following a single dose (Day 1) and at steady-state (after the final dose following multiple dosing), including but not limited to the following:

- Area under the plasma concentration-time curve from time 0 to time t (AUC_t).
- $t_{1/2z}$, as permitted by the data (single dose only [Day 1]).
- Apparent clearance after extravascular administration (CL/F).
- Apparent volume of distribution during the terminal disposition phase after extravascular administration (V_z/F).
- Accumulation ratio based on the area under the plasma concentration-time curve (AUC) from time 0 to time tau (AUC_{τ}) ($R_{ac(AUC)}$).
- Accumulation ratio based on plasma C_{\max} ($R_{ac(C_{\max})}$).
- Amount of drug excreted in urine from time 0 to time t (Ae_t).
- Fraction of administered dose of drug excreted in urine from time 0 to time t ($f_{e,t}$).
- Renal clearance (CL_R).

CSF PK parameters of TAK-071 planned for the single-dose Cohort 3 and at steady-state in Cohort 9 (after the final dose following multiple dosing), including but not limited to the following:

[figure not shown]
- CSF C_{\max} .
- Area under the CSF concentration-time curve from time 0 to 12 hours (AUC_{12}) (Cohort 3 only [Day 1]).
- Area under the CSF concentration-time curve from time 0 to 36 hours (AUC_{36}) (Cohort 9 only [Day 28]).
- The ratio of CSF AUC_{12} to the plasma AUC_{12} (CSF AUC_{12} : plasma AUC_{12}) (Cohort 3 only [Day 1]).
- The ratio of CSF AUC_{36} to the plasma AUC_{36} (CSF AUC_{36} : plasma AUC_{36}) (Cohort 9 only [Day 28]).

Plasma steady-state PK parameters of donepezil (Cohorts 10 to 12) on the last donepezil pretreatment day and after 21 daily doses of TAK-071, including but not limited to the following:

- t_{\max} .
- C_{\max} .
- AUC_{24} .
- Ratio of geometric mean steady-state AUC_{24} and C_{\max} for donepezil after 21 daily doses of TAK-071 in reference to donepezil alone and the associated 90% confidence intervals (CIs).

5.3 Exploratory/Additional Endpoints

CCI

CCI

6.0 DETERMINATION OF SAMPLE SIZE

The sample sizes chosen for the SRD and MRD parts are considered to be sufficient for evaluation of safety, tolerability, and PK of each cohort but are not based on statistical power considerations.

A sample size of 12 subjects (4 per sequence) was chosen for the 3-period, 3-sequence, crossover design in Cohort 17. The sample size is considered sufficient to assess the bioavailability of TAK-071 from the tablet relative to the capsule and to assess the effect of food on the bioavailability of TAK-071 from the tablet. This sample size was not based on statistical power considerations.

Enrolled participants who withdraw from the study for reasons other than safety may be replaced to ensure adequate numbers of evaluable subjects. The decision to replace a withdrawn subject will be made at the discretion of Takeda and the investigator.

In addition, in the event of a nonsafety-related critical procedure study interpretation (ie, CSF collection) where a subject is not withdrawn and remains in the study for the completion of all other assessments, that subject may be replaced on a case-by-case basis to ensure evaluability of that particular endpoint (ie, CSF, PK).

7.0 METHODS OF ANALYSIS AND PRESENTATION

7.1 General Principles

This Statistical Analysis Plan (SAP) was developed based on International Conference on Harmonization E3 [1] and E9 [2] Guidelines. This SAP should be read in conjunction with the study protocol and electronic case report forms (eCRFs). This version of the SAP was developed using the information provided in Protocol TAK-071-1001 Amendment 05, dated 15 May 2017 [3].

All study-related raw data, including derived data, will be presented in data listings. Continuous data will be summarized using: number of subjects (N), mean, standard deviation (SD), median, minimum, and maximum, where appropriate. Where indicated, coefficient of variation (%CV) and geometric mean will also be included in the summary of continuous data. Categorical data will be summarized using the number and percentage of subjects for each category where appropriate.

All statistical tests will be 2-tailed at $\alpha=0.05$ level for significance unless otherwise stated. The p-values less than or equal to α (when rounded to three digits) are reported as “significant”. The phrase “no significant difference” indicates that all p-values for the tests are greater than α . All computations will be performed prior to rounding.

Data collected for subjects during the study period in which they received placebo will be pooled together in all safety summaries for each cohort and will be analyzed as one placebo group.

7.1.1 Missing Data

There will be no imputation of incomplete or missing data. Decisions regarding inclusion or exclusion of data from an analysis for subjects who are noncompliant with the dose schedule, or who have incomplete data, will be made on a case-by-case basis, but the data will be presented in data listings regardless.

Plasma concentrations that are below the limit of quantification will be treated as zero in the summarizing of concentration values and deriving of PK parameters. These values will be flagged in the data listings, and deviations from this convention may be considered on a case-by-case basis as deemed appropriate.

7.1.2 Derived Datasets and Variables

Derived datasets will be generated according to Clinical Data Interchange Standards Consortium guidance documents: Analysis Data Model (ADaM) Implementation Guide, Version 1.0 (17 Dec 2009); ADaM Data Structure for Adverse Event Analysis, Version 1.0 (10 May 2012).

Body mass index (BMI) will be calculated as $\text{weight (kg)}/(\text{height (m)})^2$ and will be presented to 1 decimal place. BMI will be calculated for Screening.

7.1.3 Definition of Study Days and Baseline

For all safety endpoints, Baseline is defined as the last non-missing measurement prior to first dose of study drug for subjects in the SRD Cohorts (Cohorts 1 to 6 and 18 to 22), non-Japanese MRD cohorts (Cohorts 7 to 12) and Japanese MRD cohorts (Cohorts 13 to 15). Baseline is defined as the last non-missing measurement prior to first dose of study drug in the respective treatment period for subjects with MCI or mild AD (Cohort 16) and subjects in relative BA and FE Cohort (Cohort 17).

For all safety endpoints in the SRD Cohorts (Cohorts 1 to 6 and 18 to 22) and non-Japanese MRD cohorts (Cohorts 7 to 12) and Japanese MRD cohorts (Cohorts 13 to 15), study day will be calculated relative to the date of first dose. Study day prior to the first dose of treatment will be calculated as: date of assessment/event – date of treatment; study day on or after the date of first dose of treatment will be calculated as: date of assessment/event – date of treatment + 1. For subjects with MCI or mild AD (Cohort 16) and relative BA and FE cohort (Cohort 17), study day will be calculated relative to the date of first TAK-071 dose in the respective treatment period. Study day prior to the first TAK-071 dose in the respective treatment period will be calculated as: date of assessment/event – date of treatment; study day on or after the first TAK-071 dose in the respective treatment period will be calculated as: date of assessment/event – date of treatment + 1.

7.2 Analysis Sets

Safety Set

The safety analysis set will consist of all subjects who are enrolled and received 1 dose of study drug. Subjects in this analysis set will be used for demographic, Baseline characteristics, and safety summaries.

Pharmacokinetic Set

The PK set will consist of all subjects who receive study drug and have at least 1 measurable plasma concentration or amount of drug in the urine. All subjects with valid PK parameter estimate will be included in the summaries and analyses for that parameter.

Pharmacodynamic Set

The PD set will consist of all subjects who receive study drug and have at least 1 postdose PD measurement.

If any subjects are found to be noncompliant in dosing schedule or with incomplete data, a decision will be made on a case-by-case basis as to their inclusion in the PK and PD analysis but will be presented in the subject listings.

7.3 Disposition of Subjects

The primary reason for screen failure will be summarized.

The number and percentage of subjects who complete study drug, prematurely discontinue study drug and study visits will be summarized by the pooled placebo group, each TAK-071 dose

level, TAK-071 overall, and overall total within each part (SRD cohorts, non-Japanese MRD cohorts, Japanese MRD cohorts, Cohort 16, and Cohort 17). In addition, the number and percentage of subjects will be summarized for each reason of discontinuation of study drug and study visits by the pooled placebo group, each TAK-071 dose level, TAK-071 overall, and overall total within each part (SRD cohorts, non-Japanese MRD cohorts, Japanese MRD cohorts) and by treatment sequence and overall total for Cohort 16 and Cohort 17. Subjects' study completion data, including reasons for premature termination, will be listed for each cohort by study part (SRD cohorts, non-Japanese MRD cohorts, Japanese MRD cohort, Cohort 16, and Cohort 17) for all subjects.

The number and percentage of subjects who comprised each analysis set will be summarized by the pooled placebo group, each TAK-071 dose level, TAK-071 overall, and overall total for all subjects in each part of the study and by treatment sequence and overall total for Cohort 16 and Cohort 17.

7.4 Protocol Deviations

The protocol deviations will be provided in a data listing and summarized by the pooled placebo group, each TAK-071 dose level, TAK-071 overall, and overall total within each part (SRD cohorts, non-Japanese MRD cohorts, Japanese MRD cohorts) and by treatment sequence and overall total for Cohort 16 and Cohort 17.

7.5 Demographic and Baseline Characteristics

Demographic and baseline characteristics will be summarized by the pooled placebo group, each TAK-071 dose level, TAK-071 overall, and overall total within each part (SRD cohorts, non-Japanese MRD cohorts, Japanese MRD cohorts) and by treatment sequence and overall total for Cohort 16 and Cohort 17. Summary statistics (N, mean, SD, median, minimum, and maximum) will be generated for continuous variables (eg, age, height, weight, and BMI), and the number and percentage of subjects within each category will be presented for categorical variables (eg, gender, race, ethnicity, caffeine consumption, alcohol use, reproductive status, and smoking status).

Demographic variables of screen failure subjects and reasons for screen failures will be summarized for all subjects who are screened but not enrolled in the study. Individual demographic characteristics, date of informed consent, any available safety data and reason for screen failure will also be presented in the data listing.

7.6 Medical History and Concurrent Medical Conditions

Medical history obtained includes any significant conditions or diseases that stopped at or prior to signing of informed consent. Concurrent medical conditions are those significant ongoing conditions or diseases that are present at signing of informed consent.

For subjects in Cohort 16, the following medical history will be collected: diagnosis, date of diagnosis, Mini Mental State Examination (MMSE) score, date of onset of donepezil treatment, and dose and timing of administration of donepezil (evening [bedtime] required).

Medical history and concurrent medical condition verbatim reported terms will be coded using the Medical Dictionary for Regulatory Activities (MedDRA), version to be delineated in the clinical study report (CSR). No summaries for medical history and concurrent medical conditions will be provided. All medical history and concurrent medical conditions will be listed.

7.7 Medication History and Concomitant Medications

Medication history information obtained includes any medication stopped at or within 28 days prior to signing of informed consent. Medications used from signing of informed consent through the end of study will be considered as concomitant medications.

Medication history and concomitant medications will be coded using World Health Organization Drug Dictionary, version to be delineated in the CSR. No summaries for medication history and concomitant medications will be provided. All medication history and concomitant medications data will be listed.

7.8 Study Drug Exposure and Compliance

The date and time of each dose for each subject will be reported in the data listing for all subjects. Summaries of PK and PD data will be provided by placebo (as applicable) and TAK-071 dose level in each part of the study. No other summary statistics for the extent of exposure to study drug or compliance calculations will be performed for this study.

7.9 Efficacy Analysis

Not applicable.

7.10 Pharmacokinetic Analysis

7.10.1 Plasma Pharmacokinetic Concentrations

Collection of Blood Samples for Pharmacokinetic Analysis Cohorts 1 to 6, 18 and 19.

Analyte	Matrix	Dosing Day	Scheduled Time (hours)
TAK-071	Plasma	1	Cohorts 1 to 6: Predose (within 30 minutes before dosing) and 0.25, 0.5, 1, 1.5, 2, 3, 4, 6, 8, 10, 12, 14, 24, 48, 72, 96, and 168 hours postdose Cohorts 18 and 19: Predose (within 30 minutes before dosing) and 0.5, 1, 2, 4, 6, 8, 10, 12, 16, 32, 40, 48, 56, 64, 72, 96, and 168 hours postdose

Collection of Blood Samples for Pharmacokinetic Analysis Cohorts 7 and 8.

Analyte	Matrix	Dosing Day	Scheduled Time (hours)
TAK-071	Plasma	1	Predose (within 30 minutes before dosing) and 0.25, 0.5, 1, 1.5, 2, 3, 4, 6, 8, 10, 12, 14, and 24 hours postdose
TAK-071	Plasma	8, 14, 19, and 20	Predose (within 30 minutes before dosing)
TAK-071	Plasma	21	Predose (within 30 minutes before dosing) and 0.25, 0.5, 1, 1.5, 2, 3, 4, 6, 8, 10, 12, 14, and 24 hours postdose

Collection of Blood Samples for Pharmacokinetic Analysis Cohorts 9 and 13 to 15.

Analyte	Matrix	Dosing Day	Scheduled Time (hours)
TAK-071	Plasma	1	Predose (within 30 minutes before dosing) and 0.25, 0.5, 1, 1.5, 2, 3, 4, 6, 8, 10, 12, 14, 24, 48, 72, and 96 hours postdose
TAK-071	Plasma	8	Predose (within 30 minutes before dosing) and 0.25, 0.5, 1, 1.5, 2, 3, 4, 6, 8, 10, 12, 14, and 24 hours postdose
TAK-071	Plasma	15, 20, 26, and 27	Predose (within 30 minutes before dosing of TAK-071)
TAK-071	Plasma	28	Predose (within 30 minutes before dosing) and 0.25, 0.5, 1, 1.5, 2, 3, 4, 6, 8, 10, 12, 14, and 24, hours postdose. For Cohort 9 only, an additional sample at 36 hours postdose.

Collection of Blood Samples for Pharmacokinetic Analysis Cohorts 10 to 12.

Analyte	Matrix	Dosing Day	Scheduled Time (hours)
TAK-071	Plasma	1	Predose (within 30 minutes before dosing) and 0.25, 0.5, 1, 1.5, 2, 3, 4, 6, 8, 10, 12, 14, and 24 hours postdose of TAK -071
TAK-071	Plasma	8, 14, 19, and 20	Predose (within 30 minutes before dosing of TAK-071)
TAK-071	Plasma	21	Predose (within 30 minutes before dosing) and 0.25, 0.5, 1, 1.5, 2, 3, 4, 6, 8, 10, 12, 14, and 24 hours postdose of TAK-071
Donepezil	Plasma	-7, -3, and -2	Predose (within 30 minutes before dosing of donepezil)
Donepezil	Plasma	-1	Predose (within 30 minutes before dosing) and 1, 2, 3, 4, 6, 8, 10, 12, 14, and 24 hours postdose of donepezil
Donepezil	Plasma	8, 14, and 20	Predose (within 30 minutes before dosing of donepezil)
Donepezil	Plasma	21	Predose (within 30 minutes before dosing) and 1, 2, 3, 4, 6, 8, 10, 12, 14, and 24 hours postdose of donepezil

Collection of Blood Samples for Pharmacokinetic Analysis Cohort 16.

Analyte	Matrix	Dosing Day	Scheduled Time (hours)
TAK-071	Plasma	1, 21, 42, and 62	Predose (within 30 minutes before dosing) and 0.5, 1, 2, 4, 6, 8, 10, 12, and 24 hours postdose of TAK-071
Donepezil	Plasma	1, 21, 42, and 62	Predose (within 30 minutes before dosing of donepezil)

Collection of Blood Samples for Pharmacokinetic Analysis Cohort 17.

Analyte	Matrix	Dosing Day	Scheduled Time (hours)
TAK-071	Plasma	1 (each of 3 periods)	Predose (within 30 minutes before dosing) and 0.5, 1, 2, 3, 4, 6, 8, 10, 12, 16, 24, 32, 40, 48, 72, 96 and 168 hours postdose of TAK-071

Collection of Blood Samples for Pharmacokinetic Analysis Cohort 20 to 22.

Analyte	Matrix	Dosing Day	Scheduled Time (hours)
TAK-071	Plasma	1	Predose (within 30 minutes before dosing) and 2, 4, 8, 12, 16, 24, 25, 26, 27, 28, 30, 32, 36, 40, 48, 56, 72, 96 and 168 hours post TAK-071 dose
Donepezil	Plasma	2	Predose (within 30 minutes before dosing) and 1, 2, 3, 4, 6, 8, 12, 16, 24, 32, 36, 40, 48, 56, 72, and 144 post donepezil dose

The concentration of TAK-071 will be summarized by TAK-071 dose level, treatment, or regimen, as applicable, over each scheduled sampling time using descriptive statistics (including N, arithmetic mean, SD, %CV, median, minimum, maximum, geometric mean and %CV of the geometric mean), separately for the TAK-071 SRD part (TAK-071 alone [Cohort 1 to 6, 18, and 19]) or in presence of donepezil [Cohorts 20 to 22] for non-Japanese subjects), the MRD part (TAK-071 alone for non-Japanese subjects [Cohorts 7 to 9], TAK-071 alone for Japanese subjects [Cohorts 13 to 15], or TAK-071 in the presence of donepezil [Cohorts 10 to 12] for non-Japanese subjects), subjects with MCI or Mild AD (Cohort 16), and the relative BA/FE cohort (Cohort 17).

Similarly, the concentration of donepezil will be summarized separately for the SRD part ([Cohorts 20 to 22] for non-Japanese subjects) and the MRD part ([Cohorts 10 to 12] for non-Japanese subjects). Plasma PK parameters for donepezil will also be listed and summarized for subjects with MCI or Mild AD (Cohort 16).

Individual plasma concentration data versus time will be presented similarly in data listings. Additionally, graphical plots of individual and mean plasma concentration vs time profiles by treatment will be presented.

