6.1.1 SRD Part (Cohorts 1 to 6 and 18 to 22)

The SRD part of the study is a randomized, double-blind, placebo-controlled, parallel-group, ascending dose design involving single-dose escalation through 7 (or more, if needed) cohorts. Subjects will be confined throughout the Treatment Period (from Day -1 to Day 5), with a follow-up assessment on Day 12 (±2) days. Based on emerging preliminary PK data following Cohort 1, an additional visit for PK collection will be done on Day 8. For Cohorts 1 to 6, 18, and 19, healthy subjects will be randomly assigned to TAK-071 or matching placebo in a 3:1 ratio.

For Cohorts 20 to 22, healthy subjects will be randomly assigned to TAK-071+donepezil, donepezil, and placebo in a 2:1:1 ratio so that after completion of each cohort, 6 subjects had received TAK-071+donepezil, 3 subjects had received donepezil+TAK-071 placebo, and 3 subjects had received donepezil placebo+TAK-071 placebo.

Sentinel dosing will be used for Cohort 1 (1 subject to receive TAK-071 and 1 subject to receive placebo) to provide safety and tolerability evaluations prior to administering TAK-071 to the remainder of subjects within the cohort. After reviewing 24-hour postdose safety and tolerability data from the sentinel group, the remaining 6 subjects of the cohort may be dosed provided that the AE profile of TAK-071 in the first 2 subjects is considered acceptable. For subsequent cohorts (2, 4 to 6, 18, and 19), the intent is to stagger dosing between the first 2 subjects (1 TAK-071 and 1 placebo) and subsequent subjects dosed, starting no earlier than the median t_{max} observed in

earlier cohorts (providing that there are no issues arising in the previous cohort). Depending on the observed length of t_{max} , this could involve dosing the next day.

Sentinel dosing will be used for Cohorts 20 to 22 (1 subject to receive donepezil placebo+TAK-071 placebo, 1 subject to receive donepezil+TAK-071 placebo, and 1 subject to receive donepezil+TAK-071). After reviewing 24-hour postdose safety and tolerability data from the sentinel group, the remaining 9 subjects of the cohort may be dosed provided that the AE profile of TAK-071 in the first 3 subjects is considered acceptable.

For Cohort 3, subjects will be staggered across multiple days to facilitate CSF collection.

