6.1.2.1 Non-Japanese Subjects (Cohorts 7 to 9)

Dose escalation will progress through 3 cohorts. Subjects will be confined during the Treatment Period from Day -1 to Day 22 (Cohorts 7 and 8) or Day 29 (Cohort 9).

For Cohorts 7 and 8, healthy subjects will be randomized to receive multiple doses (21 oral doses QD) of TAK-071 or matching placebo in a 3:1 ratio.

For Cohort 9, TAK-071 or placebo will be administered as a single oral dose, followed by a 7-day washout period and then daily dosing for 21 days or matching placebo in a 3:1 ratio. The 7-day

washout period in Cohort 9 is intended to provide sufficient time to characterize the TAK-071 terminal disposition phase, but it is not expected to result in complete disappearance of TAK-071 from plasma prior to starting repeat dosing on Day 8. Nonetheless, Day 8 trough concentrations are expected to be very low (ie, <5% steady state C_{max}).

For Cohort 9, the potential for time dependency in PK will be evaluated. CSF samples will also be obtained at 5 selected time points after the dose on Day 28 via an indwelling cannula to provide an indication of brain penetration and the concentration relative to circulating plasma concentrations at steady-state of TAK-071. ^{CCI}

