4.4.2 SRD Part (Cohorts 1 to 6 and 18 to 22)

The SRD part of the study is a randomized, double-blind, placebo-controlled, parallel-group, ascending dose design involving single-dose escalation through 7 (or more, if needed) cohorts. Subjects will be confined throughout the Treatment Period (from Day -1 to Day 5), with a follow-up assessment on Day 12 (± 2) days. Based on emerging preliminary PK data following Cohort 1, an additional visit for PK collection will be done on Day 8. For Cohorts 1 to 6, 18, and 19, healthy subjects will be randomly assigned to TAK-071 or matching placebo in a 3:1 ratio.

For Cohorts 20 to 22, healthy subjects will be randomly assigned to TAK-071+donepezil, donepezil, and placebo in a 2:1:1 ratio so that after completion of each cohort, 6 subjects had received TAK-071+donepezil, 3 subjects had received donepezil+TAK-071 placebo, and 3 subjects had received donepezil placebo+TAK-071 placebo.

Sentinel dosing will be used for Cohort 1 (1 subject to receive TAK-071 and 1 subject to receive placebo) to provide safety and tolerability evaluations prior to administering TAK-071 to the remainder of subjects within the cohort. After reviewing 24-hour postdose safety and tolerability data from the sentinel group, the remaining 6 subjects of the cohort may be dosed provided that the AE profile of TAK-071 in the first 2 subjects is considered acceptable. For subsequent cohorts (2, 4 to 6, 18, and 19), the intent is to stagger dosing between the first 2 subjects (1 TAK-071 and 1 placebo) and subsequent subjects dosed, starting no earlier than the median time of first occurrence of maximum observed concentration (t_{max}) observed in earlier cohorts (providing that there are no issues arising in the previous cohort). Depending on the observed length of t_{max} , this could involve dosing the next day.

Sentinel dosing will be used for Cohorts 20 to 22 (1 subject to receive donepezil placebo+TAK-071 placebo, 1 subject to receive donepezil+TAK-071 placebo, and 1 subject to receive donepezil+TAK-071). After reviewing 24-hour postdose safety and tolerability data from the sentinel group, the remaining 9 subjects of the cohort may be dosed provided that the AE profile of TAK-071 in the first 3 subjects is considered acceptable.

For Cohort 3, subjects will be staggered across multiple days to facilitate CSF collection.

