Additional MRD cohorts may be added to fully understand safety and tolerability of TAK-071 in subjects pretreated with donepezil.

4.4.3.3 *Japanese Subjects (Cohorts 13 to 15)*

The MRD part in Japanese subjects will involve dose escalation through 3 cohorts. Subjects will be confined throughout the Treatment Period from Day -1 to Day 29. Healthy Japanese subjects will be randomized to receive a single dose of TAK-071 or matching placebo in a 5:1 ratio, followed by a 7-day washout period and multiple doses (21 oral doses QD) of TAK-071 or placebo. The 7-day washout period in Cohorts 13 to 15 is intended to provide sufficient time to characterize the TAK-071 terminal disposition phase, but it is not expected to result in complete disappearance of TAK-071 from plasma prior to starting repeat dosing on Day 8. Nonetheless, Day 8 trough concentrations are expected to be very low (ie, <5% steady state C_{max}).

PK parameters will include a determination of time to steady-state, potential for accumulation, and time dependency in PK. In addition, data will be compared with data generated in non-Japanese subjects to determine if there are any ethnic differences in human PK.

4.4.4 **Subjects with MCI or Mild AD (Cohort 16)**

Cohort 16 will have a placebo-controlled, randomized, 2-sequence, 2-period, crossover study design to investigate the safety, tolerability, and PK in 1 of the intended target populations for TAK-071 treatment (subjects with MCI or mild AD). Up to 8 subjects (minimum of 6) previously diagnosed with MCI or mild AD and receiving ongoing donepezil (10 mg) therapy or who consent to a donepezil run-in period of 5 mg dose for 28 days and titrate up to 10 mg for at least 21 days. Subjects with previous MCI/AD diagnosis who have been treated with 5 mg for at least 28 days prior to Screening may consent to a donepezil run-in period of 10 mg for at least

21 days will be enrolled in Cohort 16. Subjects will continue with their donepezil therapy during the TAK-071 Treatment Period.

Subjects will be randomized to 1 of 2 possible treatment sequences (AB or BA) before the first dose of study drug. In each period, subjects will receive 1 of 2 possible treatments as follows:

- Treatment A: TAK-071 QD for 21 days, or
- Treatment B: 21 days of matching placebo.

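### Cohorts 9 and 13 to 15: the SAP does not say whether the Day 8 predose sample (168 h) may close the single-dose profile, and as listed the Day 1 AUC-infinity and half-life rest on 96 h of data

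*SAP*

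**What the plan says.** Cohorts 9 and 13 to 15 receive one dose on Day 1, a 7-day washout, and daily dosing from Day 8. SAP 7.10.1 and protocol Table 9.e list the Day 1 samples up to "12, 14, 24, 48, 72, and 96 hours postdose". The Day 8 row is separate: "Predose (within 30 minutes before dosing) and 0.25, 0.5, 1, 1.5, 2, 3, 4, 6, 8, 10, 12, 14, and 24 hours postdose". Other places agree with that split. Protocol Figure 6.d and SAP Figure 4.d place single-dose PK on Days 2 to 5, and Table 9.s counts samples on Days 3, 4 and 5 and then a separate set of 13 on Day 8.

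Protocol 6.1.2.1 says the "washout period in Cohort 9 is intended to provide sufficient time to characterize the TAK-071 terminal disposition phase". The Day 8 trough is "expected to be very low (ie, <5% steady state" Cmax, so some drug is expected to remain.

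The SRD cohorts run longer. Cohorts 1 to 6 are sampled at "24, 48, 72, 96, and 168 hours postdose", and protocol 6.1.1 explains: "Based on emerging preliminary PK data following Cohort 1, an additional visit for PK collection will be done on Day 8". Cohorts 17 to 22 also run to 168 h.

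SAP 7.10.2 defines AUC-infinity as AUClast plus the last quantifiable concentration divided by lambda-z. It takes lambda-z from a log-linear regression over the terminal phase without naming the points, and it requires actual sampling times. It does not mention the Day 8 predose value in connection with Day 1 parameters.

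**The concern.** The washout is there to characterize the terminal phase, yet as listed its last three days contribute nothing to the single-dose parameters. Of the cohorts whose single-dose profile extends past 24 h, only these four stop at 96 h.

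Day 1 AUC-infinity is a primary PK endpoint. It is also the denominator of R_ac(AUC) and CL/F, and the reference in the time-invariance comparison (SAP 7.10.2). Cohort 9, with 6 active subjects, is the only non-Japanese MRD cohort on TAK-071 alone with Day 1 sampling beyond 24 h. Cohorts 13 to 15, with 5 active subjects each, supply the only Japanese single-dose data. If the rule is unstated, two analysts could build the Day 1 profile differently and obtain different values of a primary endpoint.

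**Working it through.** **Timing.** Day 8 predose is (8 − 1) × 24 = 168 h after the Day 1 dose. The 30-minute predose window makes it about 167.5 to 168 h.

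**The plan's own figure.** The 168 h concentration as a share of steady-state Cmax, in a one-compartment bolus model with k = ln 2 / half-life, is exp(−168k) × (1 − exp(−24k)). This gives 3.8% at 65 h, 4.8% at 100 h and 4.9% at 140 h. Its maximum at any half-life is (7/8)^7 / 8 = 4.91%. The stated limit of 5% is reproduced at full steady state.

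**Half-life range.** The documents give no estimate. Protocol 6.2.2.2 uses 65 h and 140 h as thresholds for changing the dosing duration, and I take them as an assumed range. A rough check: that section equates 80 mg single dose with 15 mg chronic dosing, a ratio of 80/15 = 5.33. Setting 1 / (1 − 2^(−24/half-life)) = 5.33 gives about 80 h. The same section expects only a 1.5-fold rise in exposure from 80 to 160 mg, so the true value could be shorter.

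**Precision of lambda-z.** SE = σ / √Sxx, where Sxx = Σ(t − mean t)².
- 24, 48, 72, 96 h: mean 60, Sxx = 1296 + 144 + 144 + 1296 = 2880.
- Adding 168 h: mean 81.6, Sxx = 12,211.
- Ratio of SEs = √(12,211 / 2880) = 2.06, whatever the error size or half-life.
- Other windows: 2.65 (48 h onward), 1.87 (14 h onward), 1.80 (12 h onward), 1.67 (last four points against last four points).

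**Extrapolated share of AUC-infinity.** Mono-exponentially this is 2^(−t/half-life), with t the last sample. The right-hand column adds absorption with tmax 4 h (protocol 6.2.2.4).

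| Half-life | Beyond 96 h | Beyond 168 h | With absorption |
|---|---|---|---|
| 65 h | 35.9% | 16.7% | 36.3% / 16.8% |
| 100 h | 51.4% | 31.2% | 51.7% / 31.4% |
| 140 h | 62.2% | 43.5% | 62.4% / 43.7% |

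**Precision of AUC-infinity.** Simulation of the SAP formula, with an assumed 10% proportional error and a window from 24 h onward, gave these within-subject CVs without and with 168 h: 9.4% and 4.5% at 65 h (2.1-fold), 18.2% and 7.7% at 100 h (2.4-fold), 29.4% and 12.4% at 140 h (2.4-fold). At 40 h the ratio is only 1.3.

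**Effect on cohort means.** With an assumed 30% between-subject CV, the ratio of SEs is √[(0.30² + a²) / (0.30² + b²)], where a and b are the CVs above. At 65 h, √(0.0988 / 0.0920) = 1.04. At 100 h, √(0.1231 / 0.0959) = 1.13. At 140 h, √(0.1764 / 0.1054) = 1.29.

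**AUClast fallback.** If kinetics do not change with time, AUC24 at steady state equals Day 1 AUC-infinity, so AUC24(ss) / AUClast = 1 / (1 − extrapolated share).
- 96 h cut: 1 / (1 − 0.363) = 1.57 at 65 h; 1 / (1 − 0.624) = 2.66 at 140 h.
- 168 h cut: 1 / (1 − 0.168) = 1.20 at 65 h; 1 / (1 − 0.437) = 1.78 at 140 h.

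**The case against.** The sampling tables are collection schedules arranged by dosing day; they do not define which concentrations enter a noncompartmental profile. The parameter rules in SAP 7.10.2 do not end the Day 1 profile at 96 h, and the stated purpose of the washout argues for using the Day 8 value. These cohorts are confined and sampled on Day 8 anyway, so no extra visit had to be written in, unlike the SRD part. This stands: a reader might infer that the plan excludes the sample or fits lambda-z over 24 to 96 h, but neither document says so.

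A reader might also infer that Cohort 1 showed 96 h to be too short. The text cites only emerging preliminary PK data.

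The size depends on assumed half-life, error and window. No lower limit of quantification is given, so whether the 168 h value is measurable at every dose cannot be checked. The SAP refers to a Clinical Pharmacology Analysis Plan that is not available here and might set point-selection rules.

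The planned ethnic comparison is exploratory, and Cohort 9 shares its schedule with Cohorts 13 to 15, so it remains like for like. The time-invariance analysis also covers Cohorts 7 and 8, whose Day 1 profile ends at 24 h with dosing continuing; using the Day 8 sample does nothing for them.

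What remains is that the listed profiles, the figures and the blood-volume table all point towards leaving the value out, and no rule corrects that.

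**Conclusion.** The point holds as an unstated rule that can be closed for free, not as a written exclusion. If Day 1 profiles are built as listed, lambda-z and half-life are about 2 times as imprecise within a subject (1.7 to 2.7 by window). The extrapolated share of AUC-infinity is higher by about 19 to 20 percentage points at half-lives of 65 to 140 h.

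A reader might take this to mean that cohort results are twice as imprecise. They are not: the SE of mean AUC-infinity grows only about 1.04 to 1.29 times under the assumed 30% between-subject CV. Within-subject error matters more in the time-invariance model, where the random subject effect removes much of the between-subject spread.

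The most consequential case is the AUClast fallback, where unchanged kinetics would look like a 1.6- to 2.7-fold time effect with a 96 h cut. Using 168 h reduces this to 1.2 to 1.8 but does not remove it. All half-life-dependent figures rest on the assumed 65 to 140 h range and on log-linear decline after 24 h.

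**What to change.** Add to SAP 7.10.1 and 7.10.2, with a matching note under Table 9.e: for Cohorts 9 and 13 to 15, the Day 8 predose concentration, at its actual time after the Day 1 dose and if quantifiable, is also the last point of the Day 1 profile for lambda-z, t1/2z, AUClast, AUC-infinity, CL/F and Vz/F, and it remains the time-zero value of the Day 8 profile.

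Using the actual time also covers an adjusted washout, which the protocol allows. The cost is one sentence; no extra blood, visit or assay is needed.
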